**Table 4**

| Situation  | Date of Event or Censoring  | Outcome |
|---|--|----------------|
| Patient is designated a medication failure (received prohibited meds or unallowable CS burst) | Date of first dose of medication leading to medication failure designation. These dates will be obtained from the date of deviation on the protocol deviation eCRF form. | Event          |
| Patient withdraws from study (no medication failure)  | Censored at date of withdrawal   | Censored       |
| Patient completes the study (no medication failure)   | Censored at last study visit   | Censored       |
| Patient dies during study (no medication failure)   | Censored at the date of death  | Censored       |

Kaplan-Meier curves of TTMF will be plotted over time.

These analyses will also be performed for the MAD Phase 1b with the exception of the statistical testing.

Time to medication failure data will be provided in a by-patient listing in the full analysis set.

### 7.2.13. Duration of Longest SRI-4 Response

Duration of longest SRI-4 response will be computed for patients who have been identified as a responder at least once based on criteria defined in Section 7.1.1. The duration of longest response will be defined as the longest period a patient meets the SRI-4 responder criteria at consecutive visits. This will be computed as the date of last consecutive SRI-4 response – date of first consecutive response + 1.

The duration of longest SRI-4 response will be analyzed using an analysis of variance (ANOVA) model with treatment group as the effect. The p-value for the difference between the BOS161721 and placebo group is based on the F-test.

The mean, SD, median, minimum, maximum, Q3, Q4, LS Mean estimate, its standard error and 90% CI will be tabulated by treatment group and for the difference between treatment groups (BOS161721 versus placebo).

If a patient has missed a visit between two scheduled visits with a response at both, the patient will be counted as having a response at the missed visit unless otherwise specified.

Duration of longest SRI-4 response will be displayed in the SRI response listing.

These analyses will also be performed for the MAD Phase 1b with the exception of the statistical testing.

### 7.2.14. Time to First BILAG A Flare or >1 BILAG B Flare through Day 210

Time to first BILAG A Flare or >1 BILAG B Flare will be computed as the event date (as described below) – randomization date + 1. If a patient is designated as a medication failure prior to or on their day 210 visit, they will be considered as having a BILAG flare (event) as of the date of first dose of the medication leading to the medication failure designation due to prohibited medication or unallowable CS burst.

Time to first BILAG A Flare or >1 BILAG B Flare will be analyzed with Kaplan-Meier methods described for TTMF and censoring as described in Table 5. Kaplan-Meier curves will be plotted over time.

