### 3.3. Sample Size Considerations

Sample size in the Phase 1b MAD part of the study is based on operational consideration.

The sample size in the Phase 2 POC study is based on the primary endpoint, SRI-4 Response at Day 210. Approximately 156 additional patients will be randomized in a 2:1 ratio to BOS161721 versus placebo to achieve 132 evaluable patients in the FAS. This assumes 24 patients will drop prior to having received treatment and an evaluable post-baseline efficacy measure. Enrollment and randomization will be monitored in a blinded fashion and increased if needed to ensure at least 132 patients are randomized into the FAS.

A total of 132 patients randomized provides more than 80% power to detect a treatment difference of 25% in SRI-4 response rates at Day 210, based on a targeted 2-sided significance level of 10% and using a 2-sided Pearson's chi-squared test. This assumes a response rate of 65% for BOS161721 and 40% for placebo, where missing data at Day 210 is carried forward

Sponsor: Boston Pharmaceuticals, Inc.  
Protocol Number: BOS161721-02  
SAP Version and Date: Version 2.0, 29Nov2018

from most recent non-missing result and patients are treated as a non-responder if a prohibited medication defined as a medication failure occurs.

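### Duration of longest SRI-4 response is compared between arms only among patients who responded at least once, so the LS-mean difference is not a treatment effect in the randomised groups and can have the wrong sign

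*SAP*

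**What the plan says.** Section 7.2.13 of SAP version 3.0 sets the population: "Duration of longest SRI-4 response will be computed for patients who have been identified as a responder at least once". The variable is "the longest period a patient meets the SRI-4 responder criteria at consecutive visits", counted as the last date minus the first date of the run, plus one day. It is "analyzed using an analysis of variance (ANOVA) model with treatment group as the effect", and "The p-value for the difference between the BOS161721 and placebo group is based on the F-test". The tabulation is to include the "LS Mean estimate, its standard error and 90% CI will be tabulated by treatment group and for the difference between treatment groups".

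Patients who never respond get no value. The section plans no analysis of all FAS patients and does not call the comparison descriptive. Only the MAD Phase 1b part is exempt from testing, so inference is intended for the Phase 2 part. Versions 2.0 and 1.0 carry the same rule, and Section 11 of version 3.0 (changes to the planned analysis) does not touch it. The endpoint stands in Section 7.2, before the exploratory endpoints of Section 7.3, and Section 2.2 of version 2.0 lists it as a secondary efficacy endpoint.

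The list of summary statistics reads "The mean, SD, median, minimum, maximum, Q3, Q4, LS Mean estimate", so Q1 is missing.

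**The concern.** Randomisation makes the arms comparable as randomised. It does not make responders on drug comparable with responders on placebo, because treatment affects who becomes a responder. A drug that works adds responders who would not have responded on placebo and who have no counterpart in the placebo group being tested. If their responses start late or are short, they pull down the drug mean. The day count sharpens this: a patient whose only response is at Day 210 scores 1 day.

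The wrong sign would show in the LS-mean difference and its CI, and a reader of the study report would take these as the effect of the drug on durability. Section 11 drops time to SRI-4 response for every study part, so in the text shown this is the remaining SRI-4 measure of how long response lasts.

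**Working it through.** **Inputs from the documents.** The sample-size section of version 3.0 is not in the text at hand, so the planning figures come from Section 3.3 of version 2.0: 132 FAS patients at 2:1 (88 and 44), two-sided 10% level, and "This assumes a response rate of 65% for BOS161721 and 40% for placebo". These are Day 210 rates.

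**The plan's own figure.** The SAP gives none for duration. Its power statement for the primary test does reproduce. The pooled rate is (57.2 + 17.6)/132 = 0.567. The standard errors are 0.0915 under the null and 0.0897 under the alternative. (0.25 − 1.645 × 0.0915)/0.0897 = 1.11, so power is 86.6% (86.3% by exact enumeration), consistent with more than 80%.

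**Who enters the F-test.** Taking 65% and 40% as ever-response rates (an assumption): 0.65 × 88 ≈ 57 drug patients and 0.40 × 44 ≈ 18 placebo patients. If 40% would respond on either arm and 25% only on drug, then 25/65 = 38% of drug responders have no placebo counterpart.

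**Means.** Assume placebo responders average 90 days. Let A be the mean on drug of those who would respond on either arm, and E the mean of the extra responders.

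- Responders-only difference = (0.40A + 0.25E)/0.65 − 90
- All-FAS difference (never-responders at 0) = 0.40A + 0.25E − 0.40 × 90

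The last column is simulated with 88 and 44 patients at two-sided 10%. The assumed SD is 45 days for those who respond on either arm, and 20, 30 or 45 days for extra responders averaging 30, 60 or 90 days.

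| E | A | Responders-only difference | All-FAS difference | Significant for placebo, responders only |
|---|---|---|---|---|
| 30 | 90 | 66.9 − 90 = −23.1 | 43.5 − 36 = +7.5 | 56% |
| 60 | 90 | 78.5 − 90 = −11.5 | 51 − 36 = +15.0 | 28% |
| 30 | 120 | 85.4 − 90 = −4.6 | 55.5 − 36 = +19.5 | 8% |
| 90 | 90 | 0 | 58.5 − 36 = +22.5 | 5% |
| 60 | 120 | 96.9 − 90 = +6.9 | 63 − 36 = +27.0 | 2% |

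In the first row the responders-only test never favoured the drug, while a rank test on all patients did so in 52% of trials; in the second row that rank test reached 65%. With equal durations the responders-only test was significant about 5% of the time each way, against 79% for the drug by the all-patient rank test.

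**Different durations.** With 121 days for those who respond on either arm, a 30-day visit grid, and extra responders at 121, 91, 61 or 31 days, the responders-only test favoured placebo in 4%, 23%, 48% and 70% of trials. A comparison of means in all FAS patients favoured placebo in at most 1%, and the drug in 80%, 60%, 38% and 21%.

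**Without equating Day 210 and ever-response.** A latent-threshold model over seven monthly visits was set to give 65% and 40% at Day 210. The sign reversed when benefit came late and within-patient correlation was 0.8 to 0.9: −2 and −10 days in responders, against about +8 days in all FAS patients. It did not reverse with late benefit at correlation 0.3 or 0.6, nor when benefit started early or ramped up (+7 to +40 days in responders, still below the all-FAS gain).

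**The case against.** The strongest reply is about weight. This is one of more than a dozen secondary efficacy endpoints. In the visible text superiority is decided only by the Day 210 SRI-4 test, type 1 error is not adjusted across endpoints, and nothing is gated on duration. SRI-4 response by visit is also compared in the FAS (Section 7.2.1 of version 2.0), so duration would not be read alone. All of this stands, and it keeps the point below the level of a threat to the trial's conclusion.

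The second reply is that any single reversal rate reflects chosen durations. That also stands, and is why a range is given.

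A reader might infer more than the documents support:

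- **That an effective drug will usually look worse.** The SAP states no durations, and under early benefit or longer responses in other patients the sign is correct.
- **That 65% and 40% are ever-response rates.** They are Day 210 rates; ever-response over monthly visits would normally be at least as high.
- **That the F-test itself points the wrong way.** It has no direction; the sign belongs to the LS-mean difference and CI.
- **That ANOVA is invalid because durations fall on a 30-day grid.** With equal responder distributions on that grid, the simulated rejection rate was 10.5% against a nominal 10%.
- **That a 1-day duration is a mistake.** It follows from the stated formula.

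None of these replies removes the selection on outcome, which needs no numerical assumption.

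**Conclusion.** Wrong as written, and it should be fixed. The planned between-arm p-value, LS-mean difference and 90% CI compare groups selected by the outcome under study, so they do not estimate a treatment effect in the randomised population. A wrong sign is possible, not inevitable. It requires the extra drug responders to have shorter runs than patients who would respond anyway, without enough lengthening of those other responses to offset this.

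The 2% to 56% range rests on assumed durations and SDs, on version 2.0 planning rates read as ever-response rates, and on 88 and 44 patients; other assumed durations gave 4% to 70%. Even with no reversal, the equal-duration case shows that the test cannot see a benefit consisting of more patients responding. The primary SRI-4 analysis is unaffected.

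**What to change.** - Make the between-arm comparison in all FAS patients, with 0 days for those who never meet SRI-4. Report the difference in mean longest-response days per FAS patient with a bootstrap 90% CI. A two-sided rank-sum or permutation p-value may accompany it.
- Keep the responders-only summary as descriptive, with no p-value and no between-arm CI.
- Do not use a Hodges-Lehmann shift as the estimate: with this many zeros it was exactly 0 in 63% of simulated trials in the scenario of the table's first row.
- Replace Q3 and Q4 in the list of statistics with Q1 and Q3, as in Section 7.2.12.2. This is a minor edit.

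The cost is SAP wording and one changed table programme. The downside is a distribution with many zeros, possibly a median of 0 in one arm, and a comparison that partly reflects response rate. The SAP should say so where the result is defined.

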#### 7.2.12.2. Time to Medication Failure (TTMF)

Medication failure is defined in Section 4.6 of the study protocol and discussed in Section 7.1.1. TTMF will be computed as the event date (as described below) – randomization date + 1.

Kaplan-Meier methods will be used to estimate TTMF for each treatment group. Estimates of median TTMF will be provided along with 90% confidence intervals. Q1 and Q3 will also be tabulated. Comparisons between treatment groups will use the two-sided log-rank test. In addition, hazard ratio (HR) estimates with 90% CIs will be calculated from a Cox proportional hazards regression analysis that includes treatment as a factor. Censoring rules are defined as in Table 4.

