## 5.3. Study Day and Duration Variables

Reference date calculations will be defined as follows, assuming non-missing dates:

- date of interest – reference date + 1 when the date of interest is on or after the reference date;
- otherwise, date of interest – reference date.

If either date is missing or incomplete, reference date calculations will not be performed. Date imputation will be performed as identified in Section 5.6.

Study day will either have a negative value if collected before dosing or a positive value if collected on or after the day of drug dosing; there will be no study day zero.

Duration of time is dependent on reference dates and will be calculated in a manner similar to that of the reference date calculation. Duration on study is defined as the end of study date – randomization date + 1. Duration of treatment is defined as treatment end date – treatment start date + 1, where treatment end date is the date of last dose of study drug.

Time-to-event endpoints are followed until first event or censoring. As a result, event time will be calculated as: event or censoring date – reference date + 1. These are further described in Section 7.

When reporting time-to-event data (Time to Medication Failure, Time to first SRI-4 Response, Time to BILAG A Flare or >1 BILAG B flare) or duration outcomes, the results (in days) above will be converted to an appropriate unit. When reporting in months it will be divided by 30.4375; for reporting in weeks it will be divided by 7; and for reporting in years it will be divided by 365.25.

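### Duration of longest SRI-4 response (SAP v3.0, 7.2.13) has no rule for runs still open at the last assessment, so its F-test confounds onset and length of follow-up with durability

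*SAP*

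**What the plan says.** SAP v3.0, Section 7.2.13, restricts the endpoint to ever-responders: it "will be computed for patients who have been identified as a responder at least once". The value is the longest stretch of consecutive responding visits, in days: "This will be computed as the date of last consecutive SRI-4 response – date of first consecutive response + 1". On the analysis: "The duration of longest SRI-4 response will be analyzed using an analysis of variance (ANOVA) model with treatment group as the effect". On the test: "The p-value for the difference between the BOS161721 and placebo group is based on the F-test". The only rule for gaps covers a missed visit with a response on both sides of it. No event or censoring status is defined.

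The neighbouring time endpoints do have one. For time to medication failure (7.2.12.2), "Kaplan-Meier methods will be used to estimate TTMF for each treatment group", and Table 4 censors completers, withdrawals and deaths. For time to first BILAG flare (7.2.14), Table 5 censors completers and withdrawals at the last BILAG flare assessment through Day 210.

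The v3.0 text of Sections 3 and 7.1.1 is not in the pages at hand, so the design figures below come from v2.0. There, Section 3.1 makes Day 210 the last efficacy visit, with Days 240 and 270 for safety only. On SRI-4 response at Day 210, Section 3.3 states: "This assumes a response rate of 65% for BOS161721 and 40% for placebo". V3.0 Section 11 drops time to SRI-4 response for every part of the study.

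**The concern.** A run still open at the last assessment is right-censored: its true length is known only to be at least what was seen. The ANOVA treats it as finished. A patient who first responds on Day k can score at most 210 − k + 1 days: 181 days if response starts at Day 30, and 1 day if it starts at Day 210. The second patient is a success on the primary endpoint, yet enters this analysis with about the shortest duration possible.

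If one arm responds earlier, or stays under observation longer, it gets longer values even when responses are equally durable in both arms. A reader of the study report would take a significant F-test on an endpoint with this name as evidence that responses last longer on drug. With time to SRI-4 response dropped, no listed time-to-response analysis separates speed of onset from durability.

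**Working it through.** **Plan's own figure.** V2.0 Section 3.3 claims more than 80% power with 132 patients, 2:1, 65% vs 40%, two-sided 10%, Pearson chi-square.
- Pooled rate = (88 × 0.65 + 44 × 0.40)/132 = 74.8/132 = 0.567.
- Null SE = √[0.567 × 0.433 × (1/88 + 1/44)] = 0.0915. Alternative SE = √(0.65 × 0.35/88 + 0.40 × 0.60/44) = 0.0897.
- z = (0.25 − 1.645 × 0.0915)/0.0897 = 1.11, giving power 86.6% (exact binomial 86.3%). The claim is reproduced. The SAP gives no expected value, SD or power for the duration endpoint.

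**Patients in response at Day 210.** 0.65 × 88 = 57 active and 0.40 × 44 = 18 placebo. These planning rates include carried-forward results, so not all would be observed responders at that visit.

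**Simulation of the SAP rule.**
- From v2.0: 88 vs 44 patients, 30-day spacing, 65%/40% at Day 210, two-sided 10%. From v3.0: the duration formula and the F-test.
- Assumed, because the SAP gives none: seven assessments (Days 30–210), no withdrawal, and a loss of response *l* per visit that is **the same in both arms**, so durability does not differ.
- Onset probability *a* per visit solves a/(a + l) × [1 − (1 − a − l)^7] = 0.65 or 0.40. At l = 0.10, a = 0.226 and 0.102.
- A run of k visits scores 30(k − 1) + 1 days.

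| Equal loss per visit | Longest runs open | BOS161721 minus placebo | F-test rejects (nominal 10%) |
|---|---|---|---|
| 5% | 86% | 11 days | 17% |
| 10% | 74% | 13 days | 24% |
| 15% | 64% | 15 days | 34% |

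Repeat runs differ by about two percentage points (19%, 24% and 32% in one). The rejections nearly always favour BOS161721.

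**Controls.** With the same response rate in both arms at 10% loss, the F-test rejects 9.8% (65% each) and 10.0% (40% each). In a simpler one-run model with the same onset pattern in both arms, it rejects 10.0%. With the same onset and 5% loss, but withdrawal of 2% vs 8% per visit and runs ended at withdrawal, it rejects 15.8%. The excess therefore comes from differences in onset or follow-up. With onset about one visit earlier on BOS161721 in the one-run model, rejection is 57%, 38%, 28% and 17% at 0, 5, 10 and 20% loss.

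**How much of the duration is onset.** The share of within-arm variance explained by onset visit is 1.00 at 0% loss, 0.48–0.75 at 5%, 0.29–0.58 at 10% and 0.13–0.35 at 20%.

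**Candidate replacement tests, same two-state model, equal loss.** Log-rank on the *longest* run with open runs censored rejects 11, 12, 14, 19 and 31% at 5, 10, 15, 20 and 25% loss. Log-rank on the *first* run stays at 9–12%.

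**The case against.** The strongest reply is that the endpoint is an observed quantity over a common window. If one arm responds earlier, its longest observed run really is longer, and the F-test is right to reject equality of that quantity. This stands, and it narrows the fault: the error lies in reading the result as durability. The name invites that reading and nothing in 7.2.13 guards against it.

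The plan also does not contradict itself here. V2.0 Section 5.3 says "Time-to-event endpoints are followed until first event or censoring", but it mentions duration outcomes apart from the listed time-to-event endpoints, so that sentence does not bind this one. The contrast with Tables 4 and 5 shows an omission, not a broken rule.

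Three stronger readings are tempting and are not supported:
- *That the ANOVA mostly measures onset.* This depends on a loss rate the SAP does not give. It fits roughly 0–5% loss per visit; at 20% onset explains a minority of the variance.
- *That a responder who withdraws is scored as having a short response.* V2.0 Sections 5.5 and 7.1.1 carry the last result forward at every visit, which could lengthen that run instead. Whether this applies in v3.0 cannot be told from the pages at hand. Neither route censors the run.
- *That adding censoring to the longest run cures the problem.* Choosing the longest of several runs makes the censoring informative, as the 31% rejection at 25% loss shows.

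Consequence is limited. This is one of many secondary endpoints with no multiplicity adjustment (v2.0 Section 4.3), and SRI-4 response by visit (v2.0 Section 7.2.1) gives some view of onset.

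**Conclusion.** The concern holds in this form: 7.2.13 has no rule for runs open at the last assessment, enters them as completed durations, and so lets onset and follow-up pass for durability. With equal durability, the v2.0 planning rates and an assumed loss of 5–15% per visit, the F-test rejects in about 17–34% of trials instead of 10%, with an apparent advantage of 11–15 days.

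These sizes rest on assumed loss rates, a constant-rate visit model, no withdrawal, and v2.0 planning figures. The direction needs only that onset or follow-up differs between arms; without such a difference there is no inflation. Under equal durability, a higher Day 210 response rate on drug implies faster onset, so the distortion arises under the trial's own planning alternative. A reader might go further and conclude that the F-test will report false durability; the documents support only that it can. The primary SRI-4 comparison is not touched.

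**What to change.** 1. In 7.2.13, relabel the day count as 'SRI-4 response time observed through Day 210'. Report it descriptively, with the number and percentage of longest runs still open at the last assessment in each arm. State whether carried-forward results count towards a run and how withdrawal ends one. Do not use the F-test as evidence of durability.

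2. If durability is to be tested, define duration of the **first** response run, not the longest. Use the Kaplan-Meier, log-rank and Cox methods already in 7.2.12.2. Censor a run that is open at the last observed (not carried-forward) SRI-4 assessment. Count a non-response visit or medication failure as the event, dated at that visit or at the failure. Dating the loss at the last responding visit instead would leave runs censored on that same day at risk for a loss nobody could have seen.

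Cost: SAP wording and one reprogrammed table with methods already planned; no new data. The median duration may not be reached, and the comparison no longer gains from earlier onset.

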**Table 5**

| Situation  | Date of Event or Censoring | Outcome |
|---|-----------------------------------|----------------|
| Patient has a BILAG A Flare or >1 BILAG B Flare (Noted as BILAG 1A/2B Flare) prior to or on their Day 210 visit | Date of first BILAG 1A/2B Flare   | Event          |

Sponsor: Boston Pharmaceuticals, Inc.  
Protocol Number: BOS161721-02  
SAP Version and Date: Version 3.0, 13Nov2020

|  |  |          |
|--|--|----------|
| Patient is designated a medication failure (received prohibited meds or unallowable CS burst) prior to or on their Day 210 visit | Date of first dose of medication leading to medication failure designation. These dates will be obtained from the date of deviation on the protocol deviation eCRF form. | Event    |
| Patient withdraws from study (no BILAG 1A/2B Flare, no medication failure) prior to or on their Day 210 visit                    | Censored at date of last non-missing BILAG flare assessment (prior to or on withdrawal) through Day 210  | Censored |
| Patient completes the study (no BILAG 1A/2B Flare, no medication failure)  | Censored at date of last non-missing BILAG flare assessment through Day 210  | Censored |
| Patient dies during study (no BILAG 1A/2B Flare, no medication failure) prior to or on their Day 210 visit                       | Censored at the day of death   | Censored |

An event will be counted once in a patient who is a medication failure and also experiences a BILAG flare. Date of event will be the date of the earlier of the two reasons.

These analyses will also be performed for the MAD Phase 1b with the exception of the statistical testing.

Time to first BILAG A Flare or >1 BILAG B Flare data will be provided in a by-patient listing in the full analysis set.

